## Recruitment

The recruitment target is for 50 participants (25 male and 25 female) to complete Phases 1-3 of the study. Withdrawals from the study will be replaced such that the targets for study completers are achieved. We will enroll 2-3 participants/month. Participants will be recruited through: the Boston Medical Center, the VA Boston Healthcare System specialty mental health clinics, the National Center for PTSD participant re-contact database, the Red Sox Foundation and Massachusetts General Hospital Home Base Program, outreach to military or first-responder organizations including our ongoing collaboration with the Boston Fire Department, and outreach to the general public (see below). Key personnel in this study provide access to PTSD patient populations at the above facilities. Specifically, our Consultant, [name]. is an investigator and Clinical Psychologist in the National Center for PTSD and is Assistant Professor in the Department of Psychiatry at Boston University School of Medicine (for which the Boston Medical Center serves as a teaching hospital) and Co-Investigator [name] is Medical Director of the Home Base Outpatient Clinic. Outreach to the general public will occur via internet bulletin boards, social media, MGH research participation websites (e.g., "Rally," "RSVP for health"), e-posting and physical postings at universities, re-contacting participants in past PTSD studies who have signed an agreement to be re-contacted (this is included in our consent forms). Notably, at the VA Boston Healthcare System alone, 6,448 male and 685 female Veterans with a documented PTSD diagnosis attended at least one appointment in FY2017. Based on our consultant [name] previous experiences recruiting participants with PTSD at the VA Boston Healthcare System, we anticipate no difficulty meeting our recruitment goal of 2-3 participants/month.

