# Retention

Any withdrawals from the study will be replaced such that a total of 50 study completers will be achieved. During the 14-day Phase 1 sleep-recording period, research staff will be in frequent contact with each participant. Participants will come to the Sleep and Anxiety Disorders lab to be instrumented for recordings on each evening prior to recording nights and they will also arrange with staff to return the equipment (usually on the following day). At each evening visit, participants will also meet with the PI or other clinical staff to complete the Columbia-Suicide Severity Rating Scale (C-SSRS) via Zoom at which time they will be asked of any difficulties they have encountered with the study procedures and will be able to solve such problems with staff assistance. As in all of our studies, participants are encouraged to call the PI 24/7 with any concerns. For additional incentive to complete all study assessments, we offer a \$100 bonus for completing the entire protocol.

When a candidate subject responds to an advertisement, they will be instructed to leave a phone number but remain anonymous until accepted into the first phase of the study. They will then be called and given a detailed description of the study. If they continue to be interested in participation, a phone screening will be conducted by one of the study investigators by a trained research assistant. Those not meeting inclusion/exclusion criteria or who choose not to participate will, therefore, remain anonymous. In the phone screening, major inclusion criteria will be confirmed and exclusion criteria ruled out based upon the candidate participant's self-report. Candidate participants' names, addresses and email addresses will be obtained if (and only if) they are determined to meet these initial inclusion/exclusion criteria and wish to participate.

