**Power analysis:** For the primary outcome in Aim 2, we will compare physiological response and fNIRS in the rLIFC between scripts for the index trauma and the associated nightmare in each of 40 subjects completing the study (i.e., dropouts will be replaced). Based on a paired t-test at the 0.05/2 two-tailed significance level (adjusting for the two outcome measures), we will have 80% power to detect an effect size of d=0.50. In order to power the hypothesis in Exploratory Aim 1, we first assume that each of 50 subjects have one nightmare and that 60% of these nightmares will occur during REM sleep. For this situation, we will have 80% power to detect whether the probability of having greater SDI-PR or rIFG HbD response to the traumanightmare, compared to the index-trauma script is 0.70 or greater for patients who had nightmares during REM sleep, and 0.30 or less for those whose nightmares were not during REM sleep, based on Fisher's exact test, at the 0.05 two-tailed significance level.

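### Primary power is computed for 40 completers, but the protocol commits to 50 and the exploratory power uses 50, so one stated power figure must change

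*Combined protocol and SAP*

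**What the plan says.** Two sections fix the sample size at 50 people who finish the study.

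- Recruitment: "The recruitment target is for 50 participants (25 male and 25 female) to complete Phases 1-3 of the study". The same section says withdrawals are replaced until the completer targets are met.
- Retention: "Any withdrawals from the study will be replaced such that a total of 50 study completers will be achieved".

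The Power analysis paragraph uses two different counts.

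- For the primary comparison (Aim 2), responses to the two scripts are compared "in each of 40 subjects completing the study (i.e., dropouts will be replaced"). The test and level follow: "Based on a paired t-test at the 0.05/2 two-tailed significance level (adjusting for the two outcome measures"). The claim is that "we will have 80% power to detect an effect size of d=0.50".
- For Exploratory Aim 1, "we first assume that each of 50 subjects have one nightmare", and it is assumed that "60% of these nightmares will occur during REM sleep". Power is again given as 80%, for response probabilities of 0.70 (REM) and 0.30 (not REM), by Fisher's exact test at the two-sided 0.05 level.

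**The concern.** The usual reason for two counts in a power section is that one is the number enrolled and the other the number left after attrition. That reading is closed here. The 40 are described as completers with dropouts replaced, and so are the 50. The documents define no smaller analysis set for Aim 2 and make no allowance for unusable recordings.

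Nor can the exploratory aim have more participants than the primary one. Its outcome is whether SDI-PR and HbD are larger for the nightmare script than for the index-trauma script, so it is built from the same Phase 3 responses. A participant without Phase 3 data contributes to neither aim.

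At stake are the planned sample size and the detectable effect of the primary comparison. Progression to Phase 3 is demanding: at least four recorded trauma-related nightmares in two weeks, at least one of them usable as a script. A team under that pressure could read the Power analysis as permission to stop at 40, which would leave the exploratory aim well below its stated power.

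**Working it through.** **Inputs, all from the Power analysis paragraph unless noted**

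- Primary: paired t-test, two-sided alpha 0.05/2 = 0.025, d = 0.50, n = 40, stated power 80%.
- Exploratory: two-sided Fisher's exact test, alpha 0.05, probabilities 0.70 and 0.30, 60% REM, n = 50, stated power 80%.
- Committed completers: 50 (Recruitment; Retention).

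**Primary comparison**

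Power = P(T > c), where T is noncentral t with n − 1 degrees of freedom and noncentrality d√n, and c is the 1 − 0.0125 quantile of the central t. The opposite tail is negligible.

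| n | df | c | 0.50 × √n | Power at d = 0.50 | d for 80% power |
|---|---|---|---|---|---|
| 40 | 39 | 2.331 | 3.162 | 79.3% | 0.504 |
| 50 | 49 | 2.312 | 3.536 | 88.5% | 0.448 |

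The stated 80% at d = 0.50 reproduces at n = 40, to rounding. It does not reproduce at n = 50, where power is 88.5 − 80 = 8.5 points higher. The 40 is therefore the number the calculation was run on, and changing that digit alone would leave a power figure that does not match.

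Variants do not rescue n = 50:

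- The normal approximation gives 90.2%.
- Using n − 4 degrees of freedom, for the three covariates of the planned regression, gives 88.4% (79.1% at n = 40).
- Relaxing alpha to 0.05 or testing one-sided only raises power, to as much as 97%.

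**Exploratory comparison**

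Group sizes are 0.6 × 50 = 30 and 20, or 0.6 × 40 = 24 and 16. Power is the sum, over all pairs of counts for which the two-sided Fisher p-value is at most 0.05, of the product of the Binomial(n₁, 0.70) and Binomial(n₂, 0.30) probabilities.

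| Completers | REM / not REM | Power, Fisher two-sided | Pooled z, two-sided |
|---|---|---|---|
| 50 | 30 / 20 | 79.5% | 81.4% |
| 40 | 24 / 16 | 62.5% | 71.7% |

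The stated 80% reproduces at 50. At 40 it falls short by 80 − 62.5 = 17.5 points, and 80% power would need probabilities of about 0.74 against 0.26. One-sided Fisher at 40 gives 72.4%. Only a one-sided pooled z test, which the plan does not state, reaches 80% (82.0%).

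**Result**

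| Single completer number | Primary power at d = 0.50 (stated 80%) | Exploratory power (stated 80%) |
|---|---|---|
| 50 | 88.5% | 79.5% |
| 40 | 79.3% | 62.5% |

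No single number supports both stated figures.

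**The case against.** Neither calculation is wrong on its own inputs; the fault lies in using two completer counts. The two resolutions are also not equally likely. Recruitment, Retention and the exploratory calculation all say 50, and only one clause says 40. If that clause is a leftover, the primary statement is conservative: 80% power for d = 0.50 is then a floor, and no power is lost. The unfavourable case needs three statements of 50 to be wrong, and even then the loss falls on an exploratory aim, while the primary comparison keeps about 79%. Stopping at 40 would also mean disregarding the sections that govern recruitment. All of this stands and limits the weight of the point. It does not remove the contradiction, since a detectable effect of 0.50 is still not the one a 50-person study has.

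It could be argued that 40 was enough for Aim 2 and that the target was raised to 50 for the exploratory aim. The text does not say so, and calling the 40 the people who complete the study counts against it.

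A further objection is that Exploratory Hypothesis 1A needs more than Phase 3 data. It also needs the sleep stage before the script nightmare, and polysomnography covers only two to four of the 14 nights. Its analysis set may therefore be smaller than the completer set, so settling on 50 does not by itself secure 80% there. The planned analysis is also an adjusted logistic regression, so 62.5% and 79.5% are powers of the planning test only. Both remarks are correct, but neither explains why the primary comparison should have fewer participants than the exploratory one.

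**Conclusion.** The point holds: the sample size conflicts with itself, and the primary power statement does not describe the study that Recruitment and Retention commit to. With 50 completers, the primary comparison has 88.5% power at d = 0.50, or 80% at d = 0.448; the stated figure understates the study's sensitivity and does no harm to power. With 40, the exploratory power is 62.5% rather than 80%, and Recruitment and Retention are wrong as well.

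These figures rest on the plan's own tests, levels, effect sizes and 60/40 sleep-stage split. They also assume that every completer supplies usable data for the aim in question. The correction should be made, but on the more likely reading it is one of statement rather than of design.

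**What to change.** State one completer number and use it in Recruitment, Retention and both parts of the Power analysis.

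- **If 50 (better supported):** replace 40 by 50 in the primary calculation and restate the result as 80% power for d = 0.45, or about 88% for d = 0.50, with a paired t-test at the two-sided 0.025 level. The exploratory figure can stay.
- **If 40:** correct Recruitment, including its 25/25 split by sex, and Retention. Restate the exploratory calculation on 24 and 16 participants as about 63% power for 0.70 against 0.30, or 80% power for about 0.74 against 0.26.
- **If an evaluable set of 40 out of 50 was intended for Aim 2:** define it, give the reason for the expected loss, and apply the same loss to the exploratory aim, which uses the same responses.

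The cost is a text correction and one restated figure. The first option needs no participants beyond the 50 already planned.

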
# SPECIFIC AIMS

Specific Aim 1: Optimize standard operating procedures for using the NINscan device in our established SDI protocol as a flexible and portable alternative to previously employed laboratory-based hardware that lacked simultaneous fNIRS capacity."

*Hypothesis* 1: "NINscan will be easily optimized for SDI assessment in the MGH psychophysiology laboratory including event marking and systems for viewing incoming data in real time."

Specific Aim 2: Compare autonomic reactivity (SDI-PR) and fNIRS activation of the LPFC during SDI of the index trauma script and a trauma-related nightmare script.

*Hypothesis 2:* SDI-PR and LPFC activations during SDI of the trauma-nightmare script will exceed activations during SDI of the index-trauma.

Exploratory Aim 1: Determine whether the sleep stage immediately prior to traumanightmare awakenings and the trauma-nightmare content determine which individuals respond more to trauma-nightmare SDI or show a greater response to index-trauma SDI.

*Exploratory hypothesis 1A:* Individuals for whom the nightmare used to create their traumanightmare script was preceded, before awakening, by REM versus NREM sleep, will show greater SDI-PR and rIFG HbD responses to the trauma-nightmare script than to the indextrauma script.

*Exploratory hypothesis 1B*: Individuals for whom the trauma-nightmare script is judged most similar to the index trauma and/or the most severely stressful by 3 independent judges will show

greater SDI-PR and rIFG HbD responses to the nightmare script, compared to the index-trauma script.

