Statistical analyses: As feasibility assessments of NINscan methodology, Hypothesis 1 The gualitative optimization of NINscan's biosensor configuration, biosignal acquisition, event marking, and interface with software delivering SDI stimuli, rather than quantitative hypothesis testing, is the focus of Aim 1. To test Hypothesis 2, the two primary outcome variables (rIFG fNIRS HbD and SDI-PR) will be compared between trauma-nightmare and index-trauma SDI using multiple regression adjusting for age, sex and duration since trauma. Secondary outcome variables (HbD from the 7 remaining fNIRS ROIs) will be compared between groups using the same regression model as for the primary fNIRS outcomes adjusting for multiple comparisons using the false discovery rate. Analysis of Exploratory Hypothesis 1A: We will investigate whether a stronger response to the trauma-nightmare as compared to the indextrauma script is associated with REM sleep using logistic regression, with REM sleep (0/1), sex (M/F) and duration since trauma as predictors. Analysis of Exploratory Hypothesis 1B: The similarity between the trauma-nightmare and index-trauma scripts and the severity of the trauma-nightmare script will be evaluated for each subject by 3 judges using 7-point Likert scales. The relationship between these evaluations and a greater SDI-PR or rIFG HbD response to trauma-nightmare than index-trauma SDI will be assessed using ordinal regression, with sex, judge ID, and duration since trauma as additional covariates.

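### The two Aim 2 primary outcomes are adjusted only by a fixed 0.05/2 split in the power paragraph; Holm would give the same error control with more power, and the 80% should be labelled per-outcome

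*Combined protocol and SAP*

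**What the plan says.** All references are to the combined protocol and SAP.

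- **Specific Aims, Hypothesis 2:** "SDI-PR and LPFC activations during SDI of the trauma-nightmare script will exceed activations during SDI of the index-trauma".
- **Statistical analyses:** "the two primary outcome variables (rIFG fNIRS HbD and SDI-PR) will be compared between trauma-nightmare and index-trauma SDI using multiple regression", with covariates. No significance level or multiplicity rule for these two tests appears in that paragraph, and nothing says whether one or both must succeed. The seven remaining ROIs do get a rule: "adjusting for multiple comparisons using the false discovery rate".
- **Power analysis:** "Based on a paired t-test at the 0.05/2 two-tailed significance level (adjusting for the two outcome measures"), and on that basis "we will have 80% power to detect an effect size of d=0.50". The sample is given as "in each of 40 subjects completing the study (i.e., dropouts will be replaced").
- **Recruitment:** "The recruitment target is for 50 participants (25 male and 25 female) to complete Phases 1-3 of the study". The Aim 2 calculation therefore uses ten fewer completers than the study plans to obtain.

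The correlation between the two outcomes is not given anywhere.

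**The concern.** The only rule for the two primary tests sits in the sample-size justification, and it is the plain Bonferroni split. Two things follow.

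First, once one outcome has passed 0.025, holding the other to 0.025 as well buys no extra family-wise protection. A second outcome with p=0.03 would be declared negative under the split and positive under Holm, with the same 5% control.

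Second, a reader who sees 80% beside a hypothesis naming both measures may take it as the chance of confirming both. It is the chance of confirming one specified measure.

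What is at stake is power on the second outcome, and a testing rule that an analyst can find in the analysis paragraph.

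**Working it through.** **Inputs.** From Power analysis: n=40, d=0.50, two-sided 0.025 per outcome, paired t-test. From Recruitment: n=50. Assumed, because the documents do not say: d=0.50 on both outcomes, and correlation r between the two difference scores from 0 to 0.8.

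**Step 1: reproduce the stated figure.** Paired t-test power comes from the noncentral t with df=n−1 and noncentrality d√n.

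- n=40: 79.3% at 0.025; 86.9% at 0.05.
- n=50: 88.5% at 0.025; 93.4% at 0.05.

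The stated 80% reproduces as a per-outcome figure. Giving up three further degrees of freedom for the three covariates moves 79.3% only to 79.1%.

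**Step 2: closed forms at r=0.** Write a for power at 0.025 and b for power at 0.05. For n=40, a=0.7934 and b=0.8694.

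- Both, fixed split: a² = 0.629.
- Per outcome, Holm: a + a(b−a) = 0.7934 + 0.7934×0.0760 = 0.854.
- Both, Holm: b² − (b−a)² = 0.7559 − 0.0058 = 0.750.
- Both, each at 0.05 (valid only if both must succeed): b² = 0.756.

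**Step 3: correlated outcomes.** Simulation with 400,000 replicates, bivariate normal difference scores; simulation error is about 0.1 point. Values are percentages.

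| n | r | Per outcome, Holm | Both, split | Both, Holm | Both, each at 0.05 | At least one (split or Holm) |
|---|---|---|---|---|---|---|
| 40 | 0 | 85.5 | 62.9 | 75.0 | 75.6 | 95.8 |
| 40 | 0.3 | 84.8 | 65.6 | 76.5 | 77.2 | 93.2 |
| 40 | 0.5 | 84.4 | 67.7 | 77.7 | 78.6 | 91.1 |
| 40 | 0.8 | 83.4 | 71.9 | 80.1 | 81.5 | 86.8 |
| 50 | 0 | 92.9 | 78.4 | 87.0 | 87.3 | 98.7 |
| 50 | 0.3 | 92.4 | 79.7 | 87.5 | 87.8 | 97.4 |
| 50 | 0.5 | 92.1 | 81.0 | 88.1 | 88.5 | 96.2 |
| 50 | 0.8 | 91.4 | 83.6 | 89.3 | 90.2 | 93.5 |

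Per-outcome power under the split is 79.3% (n=40) or 88.5% (n=50) whatever r is.

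**Step 4: error control.** With no effect on either outcome, Holm rejects something exactly when the split does. With independent outcomes that is 1 − 0.975² = 4.94%. With an effect on one outcome only, the null outcome is never tested above 0.05.

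**Step 5: effect on one outcome only, independent outcomes.** The real effect gains only when the null outcome happens to pass 0.025: (0.8694 − 0.7934) × 0.025 = 0.0019, about 0.2 points.

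**The case against.** The best defence is that nothing here is wrong. Bonferroni is valid, it was fixed in advance, and it gives simple simultaneous intervals. The 80% is accurate for what was calculated. At 50 completers, power for both outcomes under the split is already about 80%. Holm does not raise the chance of at least one success, and its gain nearly vanishes if only one outcome responds. All of this stands, and it is why the point is minor. It does not remove the case for a procedure that is never less powerful at the same error rate, nor for placing the rule where the tests are described.

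A reader might go further in two ways, and the documents support neither.

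- **That the 80% does not apply to Hypothesis 2, because its wording is a joint claim.** No section says both outcomes must succeed. The *and* can simply list what is measured, and Power analysis handles the outcomes as two separately adjusted tests. The exploratory hypotheses show how loosely the conjunction is used: the aims say participants "will show greater SDI-PR and rIFG HbD responses to the trauma-nightmare script", whereas the analysis and power paragraphs join the same two measures with *or*. Even if a joint claim were meant, it would need no split, and each test at 0.05 gives 75.6% to 81.5% at n=40.
- **That family-wise error is near 10%.** Two independent unadjusted 0.05 tests would give 1 − 0.95² = 9.75%. But Statistical analyses proposes no such tests, and the next paragraph of the same document states 0.05/2. The figure requires setting that level aside.

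**Conclusion.** The concern holds as a minor efficiency and clarity point. The fixed split is valid, and 80% is correct per outcome, but the split is stricter than 5% family-wise control requires and 80% is not the power to show both.

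With d=0.50 on both outcomes and r from 0 to 0.8, moving to Holm has these effects:

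- At 40 completers, per-outcome power rises from 79.3% to 83.4–85.5%, and power for both from 62.9–71.9% to 75.0–80.1%.
- At 50 completers, per-outcome power rises from 88.5% to 91.4–92.9%, and power for both from 78.4–83.6% to 87.0–89.3%.

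These sizes rest on the assumed correlation and on equal effects on both outcomes. The 40-versus-50 difference matters about as much as the choice of procedure.

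**What to change.** 1. **Statistical analyses:** state that the two primary outcomes are tested by Holm at family-wise two-sided 0.05. Compare the smaller p with 0.025; if it is significant, compare the other with 0.05.
2. **Hypothesis 2:** present it as two separately concluded hypotheses, one for SDI-PR and one for rIFG HbD.
3. **Power analysis:** label the 80% as per-outcome power. Add the power for both outcomes with the correlation assumed, at the number of completers actually planned.

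If the sponsor does intend that both outcomes must succeed, say so instead. Test each at two-sided 0.05 in the hypothesised direction and quote joint power: 75.6% to 81.5% at n=40, 87.3% to 90.2% at n=50, for r from 0 to 0.8.

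The cost is a few sentences, with no new data and no loss of error control. The one drawback is that simultaneous confidence intervals matching Holm are slightly less simple than Bonferroni intervals.
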